11.7 Accountability

The site Clinical Trials pharmacy/trial management team will maintain the IMP accountability records, including, but not limited to, quantity of vials received, quantity of vials dispensed and to which participant, batch number, expiry date, and quantity of vials destroyed. A patient specific dosing schedule will also be completed with date, batch number, expiry date, quantity of vials dispensed and initials of person dispensing. The IMP Management Plan will specify this in further detail.

11.8 Prescription and Dispensing of IMP(s)

The trial medication must only be used to treat participants in the HIPPO trial and should be taken from the HIPPO trial stock only. Only the PI or a person appropriately trained and assigned on the delegation log, will be allowed to prescribe the drug to the participant.

The exact procedures for dispensing Omegaven will be agreed with the Sponsor prior to site activation and clearly documented in the investigator site file and the Pharmacy Site File. Trial-specific working practices will be agreed with the Trust pharmacist in the IMP Management Plan. Each member of staff who dispenses the IMP will sign the accountability logs to document appropriate IMP tracking.

11.9 Administration of IMP(s)

Omegaven will be administered intravenously, as per description in the SmPC. Administration will be via central access as a first choice if available, and via peripheral access as a second choice. The Omegaven vial should be shaken before use as per guidelines on SmPC. Omegaven should not be given in the same intravenous line as heparin, calcium, potassium and magnesium. IMP administration will be by an appropriately trained member of the research team assigned on the delegation log.

11.10 Assessment of compliance

The dose and the duration of the drug administered will be recorded on the participant's medical notes and the electronic case report form (eCRF). If an incorrect dose is administered,

a dose is missed, or <80% of a dose is administered, a protocol deviation form should be completed.

11.11 Destruction, return, and recall of IMP(s)

Any dispensed drug will be destroyed in accordance with Barts Health Trust waste management policy. Expired or unusable drugs (e.g. due to temperature deviation) will be returned to the clinical trials pharmacy for destruction.

11.12 Management of Omegaven specific adverse events

On the occurrence of AEs which specifically relate to Omegaven, the infusion rate can be reduced or stopped if deemed necessary at the discretion of the direct care team. In case of hyper-triglyceridemia (see definition in **Table 1**) the Omegaven infusion will be stopped as soon as possible.

11.13 Concomitant medication

The infusion of Omegaven can cause a prolonged bleeding time and an inhibited platelet aggregation. Therefore, Omegaven should be administered with caution to patients requiring anticoagulant therapy, even with regard to a possible reduction of anticoagulants. Incompatibilities may also occur through the addition of polyvalent cations, e.g. calcium, especially when combined with heparin. Full details of interaction with medicinal products and other forms of interaction can be found in the SmPC. Patients will be closely monitored for any harms during the course of the intervention.

11.14 Recommended concurrent treatment

No specific concurrent treatment is necessary. Patients should receive standard care as concurrent treatment.

11.15 Prohibited medication

There are no prohibited medication and please refer to the SmPC for further details.

11.16 Study restrictions

There are no study restrictions.

11.17 Precautions regarding contraception

Patients enrolled in HIPPO will be admitted to the adult critical care unit and it would be acceptable to say there is no chance of the participant falling pregnant during the trial intervention. Due to the short half-life of the IMP, no precaution needs to be taken after the first 11 days of IMP administration.

11.18 Management of overdose

No antidote available.

12.0 Equipment and Devices

This study includes no equipment or device.

13.2 Site investigator assessment

The PI, who is also the CI for this trial, is responsible for the care of the participant, or in their absence an authorised medic within the research team is responsible for assessment of any event for:

Seriousness

Assessing whether the event is serious according to the definitions given in section 13.1.

Causality

Assessing the causality of all SAEs and SARs in relation to the study treatment according to the definition given. If the SAE is assessed as having a reasonable causal relationship, then it is defined as a SAR.

Expectedness

Assessing the expectedness of all SARs according to the definition given. If the SAR is unexpected (as per the reference safety information), then it is a SUSAR.

Severity

Assessing the severity of the event according to the following terms and assessments. The intensity of an event should not be confused with the term "serious" which is a regulatory definition based on participant/event endpoint criteria.

Mild: Some discomfort noted but without disruption of daily life

Moderate: Discomfort enough to affect/reduce normal activity

Severe: Complete inability to perform daily activities and lead a normal life

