The DLT assessment will be performed by a three-member panel comprising of two independent assessors (Consultant Gastroenterologists) and the Chief Investigator (CI) after the completion of each dosing phase. The panel will be blinded to study arm allocation (intervention or control). In the event that the CI does become unblinded, the delegated sub investigator will replace the CI on the adjudication panel.

Potential DLT events are defined as either a pre-specified AE or serious adverse event (SAE) attributable to Omegaven, as listed in **Table 1.**^{28 29} The pre-defined AEs and SAEs have been taken from the "undesirable effects" section in the SmPC for Omegaven, considering effects deemed unacceptable. Thrombophlebitis has also been added to this list and the range for hyper-triglyceridaemia adjusted based on previously published data.³⁰ To make provision to address any undesirable effects not listed in the SmPC, "Other" has been added to Table 1 as well. These are medical events of concern to the consultant in charge of direct patient care

with potential to be related to Omegaven. Patients will be monitored by senior clinicians at least twice a day as part of standard care. On occurrence of a medical event of concern, the research team will be notified and will assess the event against the US National Cancer Institute guidance document of Common Terminology Criteria for Adverse Events (CTCAE) version 5.0 ³¹, and will record a potential DLT event, if the event is determined as Grade 3 or higher (Figure 1). Following the identification of an event listed in **Table 1**, relatedness to Omegaven will be assessed to determine if the event will be classified as a DLT event.³² This will be based on a tiered assessment (WHO-UMC causality categories, **Table 2**).³³ If the predefined AEs and SAEs in **Table 1** are deemed as definitely or probably/likely related to the intervention, they will be counted towards the DLT assessment.

[figure not shown]

Figure 1 Flow diagram for "Other" DLT identification: The figure describes the steps of identification of an "Other" DLT for the HIPPO trial.

CTCAE: Common Terminology Criteria for Adverse Events

Table 1: DLTs defined for the HIPPO trial

DLT events	Description	Initial identification	Criteria	Time scale for consideration	Action (related to trial)

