Haemolysis	Widespread erythrocyte cell membrane destruction	Haemoglobin measured daily. Treating clinician requests haemolysis screen if indicated. -	- Laboratory evidence of haemolysis (e.g., direct antiglobulin test; schistocytes; decreased haptoglobin) AND - Loss of > 2 g haemoglobin within 24 hours (2 blood tests closest to 24 h apart) AND - Transfusion or medical intervention (i.e. steroids) indicated AND - No other potential cause than the intervention	Evidence of haemolysis within 24 hours of Omegaven infusion Transfusions that occur within 24 hours of diagnosis of haemolysis	- Document and contact CI
Hyper-triglyceridaemia	Elevated levels of triglycerides in blood	- Measured daily	- Triglycerides > 530.97 mg/dl (6 mmol/l) ³⁰	If occurs at any point during the infusion or within five half-lives (5 hours) of finishing the infusion	Stop infusion Document and contact CI
Reticulocytosis	Increase in circulating reticulocytes (immature red blood cells) as sign of accelerated erythrocyte production	- Measured daily.	Reticulocytes >100 x10 ⁹ /I ³⁴ AND No other potential cause than the intervention AND Need for transfusion within 24 hours of diagnosis	- Need for transfusion within 24 hours of diagnosis	- Document and contact CI
Thrombocytopenia	Deficiency of blood platelets	- Measured daily.	 Platelets <50 x10⁹ with requirement of platelet transfusion AND 	Within 24 hours of infusionTransfusions that occur within 24 hours	- Document and contact CI

HIPPO V3.0 14/02/2025 Page 19 of 62

			Absence of other causes of thrombocytopenia such as therapeutic agents (e.g. heparin), chronic diseases	of diagnosis of thrombocytopenia	
Thrombophlebitis	Inflammation in the vein in the presence of an intravenous catheter	 Identified on clinical examination by staff or by patient if conscious. Absence of documentation will be considered to indicate no concern. 	 Grade 3 (Pain at the puncture site with erythema, hardening and a palpable venous cord) OR Grade 4 (Pain at the puncture site with erythema, hardening and a palpable venous cord that is > 1 cm, with purulent discharge) 	If occurs within 24 hours of any Omegaven infusion, specific to the cannula used to infuse Omegaven.	- Document and contact CI

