The BOIN intervention algorithm for the HIPPO trial is shown in **Figure 2**. ³⁵ ³⁶ Cut-offs for the escalation and de-escalation boundaries for the DLT rate were obtained using software available at www.trialdesign.org, using the following input parameters:

- three doses
- target toxicity rate for the maximum tolerable dose 0.30 (30%)
- patients recruited in cohorts of nine,
- maximum sample size is 27
- 0.80 probability cut-off for overdose control

Upon the completion of each dosing phase (defined as at least five hours after the last patient in the phase has finished the last dose of Omegaven), the DLT rate will be computed as follows, and compared with the cut-offs shown in **Figure 2** before treating the next cohort of patients:

DLT rate = Number of patients who experienced DLT at current dose

Total number of evaluable patients treated on current dose

Following the DLT assessment and based on the DLT rate, the next nine intervention patients will either:

- 1) receive the next highest dose if the observed DLT rate on the current dose is ≤0.236
- 2) remain on the same dose if the observed DLT rate is >0.236 and <0.359
- 3) de-escalate to the next lowest dose if the observed DLT rate is >0.359

If de-escalation is indicated on the lowest dose, the next cohort of patients will continue at the lowest dose. If the probability of the observed DLT rate being greater than the target DLT is >0.80 and if at least three patients are treated at the current dose, the dose is too toxic. Therefore, this dose and any higher doses will be eliminated. If the lowest dose is too toxic, the trial must be terminated.

After the panel meeting that will be held following completion of each dosing phase, a report will be drafted and agreed on by all panel members in a timely manner. The report which will include the recommended dosing plan for the next cohort of patients will be signed off by the trial statistician within two weeks of receipt. Once these approvals are in place, the next cohort of patients will be recruited. These approvals will be filed in the ISF and TMF. Each DLT assessment report will also be reported to the Data Monitoring and Ethics Committee (DMEC) for information only.

[figure not shown]

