8.5 Blinding

This is an open label study. Therefore, no unblinding procedure is necessary. However, the independent adjudicators for DLT events will be blinded to study arm allocation. There is no requirement to unblind the independent adjudicators, as this is their only involvement in the trial.

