13.8 Sponsor medical assessment

Sponsor has delegated the responsibility for oversight of IMP safety profile and medical assessment of AEs, ARs, SAEs and SUSARs to the CI as medical assessor. The CI must review all SAEs within 72 hours of receipt. This review should encompass seriousness, relatedness, and expectedness. Day 0 for all SUSARs is when the SAE / SUSAR is received by the CI and / or coordinating team and / or Sponsor (whichever is first).

It is noted that the CI cannot downgrade the PI assessment of an event's causality. If there is disagreement between CI and PI assessment, no pressure should be placed on the PI to alter their assessment, but the CI can liaise with the site PI before the CI's final decision. The CI and PI assessment can differ.

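### The whole DLT panel is declared blinded to arm, but this cannot be relied on for the Chief Investigator's seat, and the replacement rule does not restore it

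*Protocol*

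**What the plan says.** Section 2.6 of the protocol sets up the adjudication: "The DLT assessment will be performed by a three-member panel comprising of two independent assessors (Consultant Gastroenterologists) and the Chief Investigator (CI"), meeting after each dosing phase is complete. It then says of all three members: "The panel will be blinded to study arm allocation (intervention or control"). A contingency follows: "In the event that the CI does become unblinded, the delegated sub investigator will replace the CI on the adjudication panel". An event in Table 1 counts as a DLT only if it is judged definitely or probably/likely related to Omegaven. After the meeting "a report will be drafted and agreed on by all panel members in a timely manner". That report contains the recommended dosing plan, and the trial statistician signs it off. The DMEC receives it for information only.

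Other sections give the CI further duties. Section 13.2: "The PI, who is also the CI for this trial, is responsible for the care of the participant". The PI, or an authorised medic of the research team in the PI's absence, assesses SAE causality. Under section 13.8 the sponsor delegates "medical assessment of AEs, ARs, SAEs and SUSARs to the CI as medical assessor", with review of relatedness within 72 hours of receipt. Every row of Table 1 carries the action "Document and contact CI". Section 8.4 says that the trial is open label and that allocation is recorded in the notes and known to the care team.

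Section 8.5 limits blinding to the independent adjudicators and explains: "There is no requirement to unblind the independent adjudicators, as this is their only involvement in the trial".

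**The concern.** Section 2.6 treats unblinding of the CI as something that might happen. Given the CI's other duties, it is the state to expect. The reason in section 8.5 for needing no unblinding, that adjudication is the adjudicators' only role, cannot describe the CI. Sections 2.6 and 8.5 therefore disagree on who is blinded. The replacement rule does not settle this, because it sets no blinding condition for the sub-investigator.

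The primary outcome is at stake. In critically ill patients, attributing an event to Omegaven rather than to the illness is a judgement. That judgement enters the DLT count, the count drives the dose for the next cohort, and the counts across doses give the maximum tolerable dose. A member who knows the arm and has already given an opinion on relatedness can sway a classification that all members must agree. No independent body is assigned to approve the dose decision afterwards.

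**Working it through.** **Step 1: can the CI be blinded?** The sections side by side:

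| Section | Content | Bearing on the CI |
|---|---|---|
| 2.6 | Whole panel blinded to arm | Includes the CI |
| 2.7, 13.2 | Single centre; the CI is the PI and assesses SAE causality (or an authorised medic in the PI's absence) | Site-level role |
| 13.8 | CI reviews relatedness of SAEs within 72 hours | Ordinarily before the panel, which meets after the phase ends |
| 13.6 | Events in Table 1 stay reportable despite the exemption list | Serious DLT events reach the CI as SAEs |
| 8.4 | Open label, allocation in the record | Arm is visible to anyone reading the notes |
| 8.5 | Only the independent adjudicators are promised blinding | Excludes the CI |

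The firmest conflict is between 2.6 and 13.8. Relatedness to study treatment has to be judged in an open-label trial by someone who is then meant to judge the same events blinded.

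**Step 2: the plan's own boundaries.** The target is 0.30 (section 2.6). Assuming the usual BOIN alternatives of 0.6 and 1.4 times the target (0.18 and 0.42):

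- Escalation: ln(0.82/0.70) / ln[(0.30×0.82)/(0.18×0.70)] = 0.2365. The plan has 0.236.
- De-escalation: ln(0.70/0.58) / ln[(0.42×0.70)/(0.30×0.58)] = 0.3585. The plan has 0.359.
- Elimination at n = 9 with a Beta(1,1) prior: P(rate > 0.30) is 0.65 with 3 DLTs and 0.85 with 4. With the 0.80 cut-off, elimination starts at 4, as in Table 3.

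At n = 9 the rule is therefore 2 or fewer escalate, 3 stay, 4 or more eliminate.

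**Step 3: how often one patient decides.** The number of DLTs X is Binomial(9, p), with P(X = x) = C(9,x) p^x (1−p)^(9−x). The true rates p are assumed.

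| p | P(2) | P(3) | P(4) | One fewer DLT changes the decision: P(3)+P(4) | One more DLT changes it: P(2)+P(3) |
|---|---|---|---|---|---|
| 0.2 | 0.302 | 0.176 | 0.066 | 0.242 | 0.478 |
| 0.3 | 0.267 | 0.267 | 0.172 | 0.438 | 0.534 |
| 0.4 | 0.161 | 0.251 | 0.251 | 0.502 | 0.412 |

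Direction matters. Going from 2 to 1 still escalates, and going from 4 to 5 still eliminates, so the two columns should not be merged.

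**Step 4: illustration of systematic under-attribution.** Suppose only a share s of true DLTs is judged related, so that X is Binomial(9, s×p). The values of s are assumed; the protocol gives none. At p = 0.40:

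| s | P(escalate) | P(eliminate) |
|---|---|---|
| 1.0 | 0.23 | 0.52 |
| 0.9 | 0.31 | 0.42 |
| 0.8 | 0.41 | 0.32 |
| 0.7 | 0.52 | 0.23 |

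**The case against.** The other side has good arguments.

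- Two of the three members are independent, have no other trial role, and nothing says that they see allocation. A reader might infer that the panel's blinding does not exist at all. The documents support doubt about one seat only.
- A reader might picture the CI casting a deciding vote. The protocol has no vote and no tie-break; the report is agreed by all members. The risk is influence on a consensus.
- Contacting the CI for each Table 1 event does not itself reveal the arm, because section 2.6 also screens controls for DLT events.
- Section 13.2 lets an authorised medic assess causality in the PI's absence, prescribing can be delegated, and day-to-day care is elsewhere placed with an Intensive Care Consultant. Section 2.6 also separates DLT assessment from pharmacovigilance. This weakens any claim that the CI will always know the arm. It does not remove the CI's duty under 13.8, since the same person acts in both processes.
- The protocol does provide a substitute. That the sub-investigator would be unblinded is not shown; what stands is that blinding is not required of them.
- Agreeing a dosing plan needs the Omegaven DLT rate, and a reader might infer that this forces adjudicators to be unblinded. It does not: the rate can be computed after blinded classification, and the statistician already signs off. The protocol simply leaves that order unstated.
- Some criteria mention the Omegaven cannula or stopping the infusion, which might suggest that any assessor can tell the arm. The protocol does not say what case material the panel sees, so this cannot be concluded.

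**Conclusion.** The point holds for the CI's seat. Blinding as stated in section 2.6 cannot be relied on there, section 8.5 does not promise it, and the replacement rule does not require it. The documents do not show that the two independent assessors are unblinded, or that any event would be misjudged.

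For a first cohort of nine evaluable patients at a dose, one patient's classification is decisive in 24%, 44% and 50% of cohorts if bias only removes DLTs, and in 48%, 53% and 41% if it only adds them, at assumed true rates of 0.2, 0.3 and 0.4. These are shares of cohorts close to a boundary. They say nothing about how often a borderline event occurs or is misclassified. At the highest dose, 2 versus 3 does not alter the next-dose decision, because there is no higher dose. The sponsor should correct this before the first panel meeting; it affects the credibility of the primary outcome but does not invalidate the design.

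**What to change.** In section 2.6, have the two independent assessors classify events and relatedness by agreement, from masked case summaries. The CI or a delegate supplies the summaries but does not classify. Any substitute assessor must have no care, prescribing or SAE-assessment role in the trial. Specify what the summaries contain, since several Table 1 criteria and the causality categories refer to the infusion.

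Then fix the order of work. The classifications are locked; the trial statistician links them to arm, computes the Omegaven DLT rate and applies Table 3; only then is the dosing report drafted. Align sections 2.6 and 8.5 on who is blinded and until when.

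The cost is protocol and panel-charter wording, plus the effort of preparing masked summaries; no extra staff are needed. The downside is that the CI loses input into the classification and two assessors must resolve disagreements by consensus. Counting every disagreement as a DLT is not proposed. That would be a new rule feeding escalation, elimination and termination, and its effect on the design has not been examined.

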13.3 Reference Safety Information

Reference safety information can be found in the SmPC under section 4.8.

13.4 Notification and recording of Adverse Events (AEs) or Reactions (ARs)

All AE and ARs unless listed in section 13.6, are to be documented in the participants' medical notes and the eCRF. Participants will be followed up by the research team until resolved.

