6.2 Exclusion criteria

We are specifically not excluding patients with acute life-threatening conditions such as collapse or shock, recent cardiac infarction, stroke, embolism, undefined coma status, severe haemorrhagic disorders or severe liver or renal insufficiency as indicated in the SmPC. We seek to test the safety of Omegaven in critically ill patients (who suffer from these conditions) as part of a new set of indications. The SmPC notes that some of these are considered contraindications as a result of lack of experience, which we seek in this safety trial to inform. In previous studies, Omegaven has been given therapeutically to critically ill patients before, in the UK ^{19 20}, and in- and outside the EU^{17 18 22 23}, but safety data are scarce. A safety trial such as the one we are proposing is necessary prior to a larger efficacy trial.

Exclusion criteria (as defined in the patient's medical notes):

- Patients requiring total parenteral nutrition at time of enrolment or during the first 10 days.
- Palliative care admission for end-of-life care or withdrawal of active therapy as determined by the Intensive Care Consultant with clinical responsibility for patient care.
- Neutropaenia (<1x10⁹/l) on admission to the Adult Critical Care Unit
- Lymphopenia (<0.25x10⁹/l) on admission to Adult Critical Care Unit
- Primary immune deficiency
- Bone marrow transplant recipient
- All immunosuppressive drug therapy (with the exception of corticosteroid use for acute illnesses in the preceding five days)
- Recorded or reported allergy to fish, or egg protein or to any of the active ingredients or excipients
- Known inborn errors of lipid metabolism

- Recorded or reported severe hyperlipidaemia or severe disorders of lipid metabolism
- Electronic health record documentation ± clinical concern and if available: serum triglycerides >400 mg/dl on admission to the Adult Critical Care Unit
- Enrolment in any other study with an IMP or a study that may have similar primary outcome
- Therapeutic anti-coagulation therapy
- Pregnancy

The absence of the above criteria in the medical notes will be considered to indicate no concern.

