13.6 AEs that do not require reporting

AEs or SAEs that are expected and do not require reporting for this trial are taken from the SmPC. However, AEs and SAEs that are defined as DLT events (Table 1) will be reported.

Similarly, considering that all eligible patients are critically ill and at increased risk of experiencing multiple AEs, the below list defines possibly and definitely expected AEs or SAEs related to organ failure and critical illness which are exempt from regulatory reporting.^{11 43}

AEs or SAEs not requiring reporting in this trial:

Prolonged bleeding time, fishy taste, headaches, circulatory effects (e.g. hypo/hypertension), rash, abdominal pain, nausea, vomiting, rise in body temperature or fever, shivering, chills, tiredness, transient increase in liver function tests, metabolic overload symptoms (hepatomegaly with or without icterus, change in reduction in bleeding time, coagulation time, prothrombin time, splenomegaly, headache, stomach pains, fatigue, hyperglycemia), dyspnoea, chest pain, hypoxaemia, rapid pulse, rapid respiratory rate, dizziness, syncope, altered mental status, seizure, confusion, anxiety, generalised weakness, anorexia back pain, constipation, pneumonia, skin infection, cancer, electrocardiography abnormalities (atrial arrhythmias, right bundle branch block, and ST and T wave changes), elevated troponin level, elevated BNP or NT ProBNP level, high white cell count, pulmonary infiltrate, pleural effusion, cardiomegaly, shock, worsening organ failure, or sepsis.

13.7 Notification and reporting of Serious Adverse Events (SAEs) and Suspected Unexpected Serious Adverse Reactions (SUSARs)

All SAEs, apart from those listed in 13.6 and SUSARs will be recorded in the participants' notes, the eCRF, the sponsor SAE form and reported to the sponsor (administered by the Joint

Research Management Office (JRMO) or agreed representative) and the IMP provider (as per contract with the funder/manufacturer) within 24 hours of the site becoming aware of the event.

Nominated co-investigators (as listed) will be authorised to sign the SAE forms in the absence of the PI at the participating site.

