15.9 Safety analysis

Frequencies and type of AEs will be recorded for each randomised group (control and intervention), and each dose level of Omegaven.

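### Sections 13.4 and 13.7 turn the 13.6 exemption from regulatory reporting into an exemption from eCRF recording, so listed sub-DLT events will be missing or unevenly counted in the 15.9 safety table by dose

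*Protocol*

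**What the plan says.** Section 13.6 gives two grounds for its list. One is the product information: "AEs or SAEs that are expected and do not require reporting for this trial are taken from the SmPC". The other is critical illness, with the events described as "related to organ failure and critical illness which are exempt from regulatory reporting". Both grounds concern reporting. The items are printed as one undivided list, which includes "transient increase in liver function tests, metabolic overload symptoms (hepatomegaly with or without icterus" and goes on to splenomegaly. It also names prolonged bleeding time, rash, nausea, vomiting, abdominal pain, shivering and chills. One group is brought back in: "However, AEs and SAEs that are defined as DLT events (Table 1) will be reported".

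Section 13.4 sets the recording rule by reference to that list: "All AE and ARs unless listed in section 13.6, are to be documented in the" medical notes and the eCRF. Section 13.7 excepts the same list from the rule that SAEs go into the notes, the eCRF and the sponsor form.

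Section 15.9 plans the safety analysis with no exclusion: "Frequencies and type of AEs will be recorded for each randomised group (control and intervention), and each dose level of Omegaven". Section 6.2 states the aim: "We seek to test the safety of Omegaven in critically ill patients".

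**The concern.** An exemption from reporting spares the site and sponsor paperwork on expected events. An exemption from recording removes data. The protocol justifies only the first but puts the second into effect. No later analysis plan can tabulate events that nobody was required to enter.

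The affected items matter here. Section 11.13 says the infusion can prolong bleeding time. Section 1.3 mentions lipid overload syndrome when justifying the highest dose, which is three times the lowest (0.6 / 0.2 g/kg/day). Section 6.2 says safety data are scarce. Critical illness also produces many of the listed events, so comparison with the randomised controls is the natural way to separate drug effect from background. Waiving recording in both arms weakens exactly that comparison.

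Oversight depends on the same data. Section 24.3 asks the DMEC to look for patterns that single cases would not reveal, and section 14.1 asks for a risk-benefit analysis covering all events. Neither can rely on events that are exempt from documentation.

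**Working it through.** The protocol states no figure on this point, so the check is a reconciliation of its text, followed by a short calculation for scale.

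**1. Scope of the exemption**
- 13.6: reporting, with regulatory reporting named.
- 13.4: documentation of AEs and ARs in the notes and eCRF.
- 13.7: documentation of SAEs in the notes and eCRF, as well as reporting.
- 15.9: frequencies and types of AEs by arm and dose, with nothing excluded.

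The first is narrower than the second and third. The fourth assumes data that the second and third do not require.

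**2. What other routes still capture**
- *Table 1 DLT events.* Section 2.6 says these were also drawn from the undesirable effects in the SmPC, and 13.6 keeps them reportable. The thresholds are high: urticaria, for example, needs more than 30% of body surface and an IV intervention.
- *The Other row of Table 1.* This needs concern on the part of the consultant, CTCAE grade 3 or higher, and onset during the infusion or within five hours of its end.
- *Daily measurements (2.6).* Liver enzymes, bilirubin, glucose, triglycerides, blood count, coagulation tests, heart rate, blood pressure, temperature and respiratory rate are noted in the CRF. DLT screening also covers controls on days 1-11.
- *AEs of special interest (13.5).* Not applicable, so this route adds nothing.

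**3. What is left uncaptured**
- Listed items with a daily CRF counterpart: fever (temperature), hypertension and hypotension (blood pressure), rapid pulse, rapid respiratory rate, hyperglycaemia (glucose), prothrombin time, icterus (bilirubin), liver function test rises. These are lost as adverse events but kept as data.
- Listed items without one: hepatomegaly, splenomegaly, rash below the urticaria threshold, nausea, vomiting, abdominal pain, shivering and chills, fishy taste. Bleeding time itself is not among the daily coagulation tests, which are prothrombin time, PTR/INR and activated partial thromboplastin time.

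The second group, below the DLT thresholds, has no required entry anywhere that would feed 15.9.

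**4. Scale (illustration; the event rates are assumptions)**

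Section 15.1 gives nine as the minimum number treated at a dose. The chance of at least one event among n patients at true rate p is 1 − (1 − p)^n. With n = 9:
- p = 10%: 1 − 0.9^9 = 0.613
- p = 20%: 1 − 0.8^9 = 0.866
- p = 30%: 1 − 0.7^9 = 0.960

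A genuine 0 of 9 has an exact two-sided 95% upper limit of 1 − 0.025^(1/9) = 33.6%. A zero that arises because recording was waived supports no such limit.

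**The case against.** The strongest reply is that the exemption is deliberate. Patients this ill have many adverse events, 13.6 says so and cites sources, and recording everything would swamp the site. The more serious product effects are captured as DLTs, and the laboratory and vital-sign data are richer than an adverse event table. Many participants will be intubated or lack capacity, so nausea, taste or abdominal pain often could not be elicited anyway.

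Much of this stands. It justifies not reporting these events and not recording every complication of critical illness. It does not explain why signs such as hepatomegaly, rash or vomiting go unrecorded when 15.9 promises a table by dose.

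A reader might go further and infer that the product's listed side effects are kept out of the eCRF altogether and that 15.9 will show them as absent, for instance as 0 of 9. The protocol does not support that. Table 1 events come from the same product information and are reported. Fever and circulatory effects survive as daily measurements. Section 13.4 waives entry but does not forbid it, so patchy counting is as likely as zeros. Nor is the adverse event table the only safety information by dose beyond the yes/no DLT: the daily measurements, SOFA score, transfusions and mortality are also collected.

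**Conclusion.** The inconsistency is real but bounded. Sections 13.4 and 13.7 extend a reporting exemption to recording, and 15.9 ignores the consequence. The loss falls on listed events below the Table 1 thresholds that have no daily CRF measurement; for these, the comparison across doses and with control will be incomplete or inconsistent. The BOIN dose decisions and the maximum tolerable dose are unaffected, because DLT events are captured separately.

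The size in lost events cannot be stated, because the protocol gives no incidence for any listed effect. The 61%, 87% and 96% figures show only that effects at assumed rates of 10% to 30% would usually occur at least once in a cohort of nine; they also presume that each event could be detected. That the list derives partly from the SmPC rests on the protocol's own statement. This should be corrected before recruitment, since the data cannot reliably be recovered afterwards.

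**What to change.** 1. In 13.6, state that the exemption covers expedited or regulatory reporting only. Align 13.4 and 13.7 so that neither uses the list to waive eCRF entry of the items named below.
2. Because 13.6 does not separate product effects from critical-illness events, name the items to be recorded: prolonged bleeding time, rash, nausea, vomiting, abdominal pain, shivering or chills, hepatomegaly, splenomegaly and the other metabolic overload symptoms. Record each in the eCRF with severity and date, in both arms, during the medical record review already scheduled for days 1-11 (8.1).
3. In 15.9, tabulate these items by dose against control, alongside by-dose summaries of the CRF laboratory and vital-sign data. State that general critical-illness events left unrecorded are not counted.

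The cost is a short checklist and modest extra data entry for 36 patients. Subjective symptoms will often be unobtainable in sedated patients, so the form should distinguish not assessable from absent.
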